2.0		 Updated the Study Operation Manager in the section of AUTHORIZED SIGNATURES Increased the sample size of the Control arm from a minimum of 8 subjects to completed to 15 to complete in sections of SYNOPSIS, 3.4 Enrollment Strategy and 4.3 Enrollment Target and Study Duration. Updated the sample label in Section 6.4. 	07-Feb-2018
3.0		 Specified in Section 7.2 Detailed Study Procedure Visit 1 Step 1.1 that corneal topography will be collected on OD for the Test group subjects and better OK treated eye for the Control group subjects. Specified in Section 15 Data Handling and Record Keeping/Archiving the external data sources. Added Corneal Topography 	05-Jun-2018

SYNOPSIS

Protocol Title	Evaluation of On-eye Optical Performances of the RMY-100 Lens
Sponsor	JJVC, [name]
Clinical Phase	Development phase, Phase 1
Trial Registration	The study will be registered on clinicaltrial.gov based on the following: This clinical study aims to understand the fundamental mechanisms of optical interventions for myopia control. The results of this study are expected to be published in peer-reviewed journals. In addition, this study will be conducted in Canada, clinicaltrial.gov registration is required by Health Canada.
Test Article(s)	Investigational Products: RMY-100: Daily disposable soft contact lens made in etafilcon A material with an optical design for myopia control.
Wear and	Wear Schedule: Daily wear
Replacement Schedules	Replacement Schedule: Daily disposable Subjects will wear the investigational test article during the study visits only. No study lenses will be dispensed for subjects to wear outside the office.
Objectives	The primary objective of the study is to evaluate the on-eye optical performances of the RMY-100 lens and compare with eyes treated with orthokeratology. The secondary objective of the study is to compare on-eye optical performances of the RMY-100 lens with eyes wearing sphero-cylindrical correction lenses in the spectacle trial frame.
Study Endpoints	 Primary endpoint: Wavefront aberrations measured at distance (0.25 D target vergence) and near (4 D target vergence) Secondary endpoint: Off-axis refraction at both temporal and nasal fields of retina at ±10°, ±20°, ±30° with targets at 4 meters and ±30° only with targets at 25 cm. Other observations: Corneal and test article on-eye topography On-axis accommodative response with target vergence of 0.25 D, 1 D, 2 D, 3 D and 4 D Slit lamp findings LogMAR visual acuity under HLHC, LLHC, and HLLC conditions Lens fit assessment Subjective vision assessment (CLUE Vision questionnaire)
Study Design	This is a two-arm parallel, non-masked, bilateral, non-dispensing study with one Test arm and one concurrent, non-randomized Control arm.

	For subjects enrolled in the Test arm, investigational test articles will be bilaterally fitted to the subject's eyes. Concurrently, a smaller sample of subjects who are established orthokeratology lens wearers will be enrolled to Control arm. Endpoint measures will be collected over one eye only (Test arm: OD only; Control arm: better OK fitted eyes).
	For subjects in the Test arm, there will be a total of 2 visits: Visit 1: Screening, baseline endpoint measures with bare eye/spectacles Visit 2: Lens fitting, endpoint measures over the study lenses and final evaluation.
	For the Control arm, subjects will be recruited through referrals from the university optometry clinic and independent Eye Care Professionals (ECPs) who will identify potential subjects by reviewing the case history of existing orthokeratology treated patients in their practices. Only subjects with complete pre-treatment record, e.g., spherocylindrical refraction and corneal topography will be invited to participate in the study.
	For subjects in the Control arm, there will be a total of 1 visit: Visit 1: Screening, baseline and endpoint measures over the selected eyes.
	See the flow chart at the end of the synopsis table for the schematic of the study visits and procedures of main observations (Figure 1).
Sample Size	Approximately 25 subjects will be enrolled in the Test arm of the study with a minimum of 20 subjects targeted to complete the study.
	Approximately 20 subjects will be enrolled in the Control arm of the study with a minimum of 15 subjects targeted to complete the study.
Study Duration	The total duration of the study is estimated to be about 14 weeks, including an approximately 10-week enrollment period.
Anticipated Study Population	Healthy male and female subjects between 7 and 25 years of age (inclusive) (prefer 7-15 if available within timeline) with best sphere refraction between -1.00 D to -5.00 D (inclusive) and 1.00 D or less astigmatism.
Eligibility Criteria	 Potential subjects must satisfy all of the following criteria to be enrolled in the study: Inclusion Criteria after Screening: Pediatric subjects (<18 years old) must read (or be read to), understand, and sign the Statement of Information and Assent and receive a fully executed copy of the form. Adult subjects (≥18 years old) and parent(s) or legal guardian(s) of pediatric subjects must read, understand and sign the Statement of Informed Consent and receive a fully executed copy of the form.

3. Appear able and willing to adhere to the instructions set forth in this
A Botween 7 and 25 years of age (inclusive)
 Detween 7 and 25 years of age (inclusive). Have normal aves (i.e., no equiprimediations or infections of any.
5. Trave normal eyes (i.e., no ocular medications of milections of any type)
type).
Below inclusion criterion is for subjects to be enrolled to the Control group only:
6. Are existing orthokeratology patients whose current treatment has been stabilized for at least 1 months and with complete pre- treatment record, e.g., spherocylindrical refraction and corneal topography. Pre-treatment wavefront aberration measures are preferred by not required.
Inclusion Criteria after Baseline (apply to subjects to be enrolled to the Test group and to Control group subjects regarding their pre-OK treatment):
 7. Vertex-corrected distance subjective best-sphere refraction must be between -1.00 D and -5.00 D (inclusive) in each eye.
8. Cylindrical refraction must be 1.00 D or less in each eye, by
subjective sphero-cylindrical refraction.
9. Have sphero-cylindrical best-corrected visual acuity of 20/25 or better in each eye.
Potential subjects who meet any of the following criteria will be
excluded from participating in the study:
Exclusion Criteria after Screening:
1. Currently pregnant or lactating.
2. Any systemic allergies, infectious disease (e.g., nepatitis, tubergulagia) autoimmuna disease (e.g., repatitis) or
other diseases, by self-report, which are known to interfere with
3 Use of systemic medications (e.g., chronic steroid use) that are
known to interfere with contact lens wear and/or participation in the study
4. Any current use of ocular topical medication (occasional use of rewetting drops is allowed)
 Any previous or planned ocular or intraocular surgery, including refractive surgery
 6. Participation in any contact lens or lens care product clinical trial within 7 days prior to study arrollment
7 Employee or their children/relatives of investigational clinic (e.g.
Investigator, Coordinator, Technician).
Below exclusion criteria are for subjects to be enrolled to the Test group only

	8. Current or recent (within 30 days from enrollment) rigid lens
	wearers.
	9. History of orthokeratology treatment.
	 Exclusion Criteria after Baseline: 10. Any ocular allergies, infections or other ocular abnormalities that are known to interfere with contact lens wear and/or participation in the study. This may include, but not be limited to, aphakia, uveitis, ocular hypertension, glaucoma, severe keratoconjunctivitis sicca, history of recurrent corneal erosions, keratoconus, keratoconus suspect, pellucid marginal degeneration, entropion, ectropion, extrusions, chalazia, and recurrent styes. 11. Any Grade 3 or greater slit lamp findings (eg, edema, corneal neovascularization, corneal staining, tarsal abnormalities, and conjunctival injection) on the FDA scale. 12. Any ocular abnormality that is contraindicated contact lens wear. 13. Any corneal scar within central 5 mm. 14. Binocular vision abnormality, intermittent strabismus or strabismus.
	 Below exclusion criteria are for subjects to be enrolled to the Test group only 15. Any corneal distortion resulting from ocular diseases or previous hard or rigid gas permeable contact lens wear.
Disallowed Medications / Interventions	Any current use of ocular topical medication such as eye drops (occasional use of re-wetting drops is allowed) and ointments. Any medication and therapies that would normally contraindicate contact lens wear.
Measurements and	For the Test group, all measurements will be taken over bare eye;
Procedures	sphero-cylindrical spectacle trial lenses and the test articles for OD
	only, and for the Control group, over bare eye for the better orthokeratology treated eye only, under binocular viewing conditions, unless otherwise specified:
	• Wavefront aberrations measured with target at distance (4 meters) and near (25 cm).
	• Off-axis refraction at both temporal and nasal fields of retina at $\pm 10^{\circ}, \pm 20^{\circ}, \pm 30^{\circ}$ with targets at 4 meters and $\pm 30^{\circ}$ only with targets at 25 cm.
	• On-axis accommodative response with target vergence of 0.25 D, 1 D, 2 D, 3 D and 4 D
	• Slit lamp findings (OD, OS)
	• LogMAR visual acuity under HLHC, LLHC, and HLLC conditions
	• Lens fit assessment (OD, OS)

	• Subjective vision assessment (CLUE Vision questionnaire)
Microbiology or	None.
Other Laboratory	
Testing	
Study Termination	The occurrence of one or more Unanticipated Adverse Device Effect (UADE), or any SAE where relationship to study agent cannot be ruled out, will result in stopping further dispensing investigational product. In the event of a UADE or SAE, the Sponsor Medical Monitor may unmask the treatment regimen of subject(s) and may discuss this with the Principal Investigator before any further subjects are enrolled.
Ancillary	None.
Supplies/	
Study-Specific	
Materials	
Principal	A detailed description of the principal Investigator, the clinical site,
Investigator and	and the institution is kept separately from the Study Protocol and is
Study Institution /	included in the study Trial Master File.
Site	

COMMONLY USED ABBREVIATIONS AND DEFINITIONS OF TERMS

ADD ADE AE BCVA BSCVA CFR CLUE COAS COM CRA CRF CSF CRO CT	Plus Power Required for Near Use Adverse Device Effect Adverse Event/Adverse Experience Best Corrected Visual Acuity Best Spectacle Corrected Visual Acuity Code of Federal Regulations Contact Lens User Experience Complete Ophthalmic Analysis System Clinical Operations Manager Clinical Research Associate Case Report Form Contrast Sensitivity Function Contract Research Organization
D	Diopter
DMC	Data Monitoring Committee
eCRF	Electronic Case Report Form
EDC	Electronic Data Capture
ETDRS	Early Treatment Diabetic Retinopathy Study
FDA	Food and Drug Administration
GCP	Good Clinical Practice
HIPAA	Health Insurance Portability and Accountability Act
IB	Investigator's Brochure
ICF	Informed Consent Form
ICH	International Council for Harmonization
IDE	Investigational Device Exemption
IEC	Independent Ethics Committee
IRB	Institutional Review Board
ISO	International Organization for Standardization
ITT	Intent-to-Treat
JJVC	Johnson & Johnson Vision Care, Inc.
LC	Limbus Center
LogMAR	Logarithm of Minimal Angle of Resolution
MedDRA [©]	Medical Dictionary for Regulatory Activities
MOP	Manual of Procedures
NIH	National Institutes of Health
OD	Right Eye
OHRP	Office for Human Research Protections
OHSR	Office for Human Subjects Research
OS	Lett Eye
UU DD	Both Eyes
PD	Protocol Deviation
PHI	Protected Health Information

PI	Principal Investigator
PIG	Patient Instruction Guide
PQC	Product Quality Complaint
PRO	Patient Reported Outcome
QA	Quality Assurance
QC	Quality Control
SAE	Serious Adverse Event/Serious Adverse Experience
SAP	Statistical Analysis Plan
SAS	Statistical Analysis System
SD	Standard Deviation
SOP	Standard Operating Procedure
UADE	Unanticipated Adverse Device Effect
USADE	Unanticipated Serious Adverse Device Effect
VA	Visual Acuity
	-

1. INTRODUCTION AND BACKGROUND

Among various optical interventions, orthokeratology (OK) has consistently shown to be effective in controlling myopia progression in clinical trials.⁴⁻¹⁵ It is commonly believed that OK controls myopia progression through introducing positive power in the periphery of the cornea relative to the center power. Such optical intervention has shown to shift the retinal image shell to the myopic direction, therefore, potentially eliminating retinal hyperopic defocus as a growth signal to the eye.¹⁶⁻²³ With the hypothesis that the effectiveness of OK for myopia control is primarily optical driven, Johnson & Johnson Vision Care Myopia Control Platform developed the RMY-100 lens that is a soft contact lens with an optical design simulating the optical impact of an OK lens to the eye (the SimOK design). The safety and effectiveness of RMY-100 lens for controlling myopia progression was evaluated in The results of the study indicated that axial elongation of the eye in the RMY-100 lens treated group was about 9% less than the spectacle lens control group. Although statistically significant, the magnitude of the effect was deemed clinically insignificant. In

addition, there was no statistically significant difference in refraction change from baseline between the two study groups. Therefore, RMY-100 lens that simulates the optical impact of orthokeratology was largely ineffective in controlling myopia progression.²⁵

Per the learning of the study is designed with the objective of evaluating the on-eye optical performances of the RMY-100 lenses and comparing to the optical characteristics of eyes undergone orthokeratology treatment and with spectacle lens correction. The results of this study may provide information towards understanding of the mechanisms of orthokeratology for controlling myopia progression.

1.1. Name and Descriptions of Investigational Products

This study will test one investigational lens (RMY-100). The RMY-100 lens is a spherical soft contact lens with an aspheric optical design aimed to control myopia progression.

The RMY-100 lens is made of the same material and with the same manufacturing process as the marketed 1 Day Acuvue[®] Moist contact lenses. The diameter and base curve of the lens fall within the US FDA cleared range of VISTAKON[®] (etafilcon A) contact lenses parameters. Further details about the test articles are found in Section 6 of this protocol.

1.2. Intended Use of Investigational Products

The intended use of the investigational test article is for daily disposable wear for correcting myopia and controlling the progression of myopia. During this study, each subject will wear the test article binocularly at the second visit of the study only, for no more than 3 hours. This is a non-dispensing study; no study lenses will be dispensed to the subjects to wear outside the study site.

1.3. Summary of Findings from Nonclinical Studies

All previous pre-clinical findings were deemed satisfactory prior to proceeding with clinical trials on humans. For the most comprehensive nonclinical information regarding the RMY-100 lenses refer to the latest version of the Investigator's Brochure for the RMY-100 lens.²⁶

1.4. Summary of Known Risks and Benefits to Human Subjects

The benefit of controlling myopia progression is considered to be substantial²⁷ as the prevalence and incidence of myopia has been increasing substantially over the past few decades.²⁸⁻³⁰ In addition, significant health risks have been associated with myopia, including glaucoma, cataract, retinal detachment and myopic macular degeneration. Therefore, it can be considered most advantageous to control the progression of myopia and start treatment at an early age when myopia is at a low level. Based on theoretical predication, it is estimated that an effect of reducing myopia progression by 33% and 50% will result in a reduction in risk population (defined as the percentage of myopes being 5.00 D or higher) by 73% and over 90%, respectively.³¹

The risks associated with the wear of contact lenses for myopia control includes 1) contact lens risks in general population; 2) contact lens risks in pediatric population; and 3) risks specifically associated with the RMY-100 lens, such as potential sub-optimal visual performances and long-term physiological and/or neurological impact. The assessment regarding the above identified risks concluded that the risks associated with the RMY-100 lens are expected to be the same as those normally attributed to the wear of soft hydrophilic contact lenses on a daily wear basis. In addition, the daily disposable modality of the investigational lenses further reduces risks associated with lens care and the use of care products (eg, cleaning, disinfecting, rinsing and storage, etc.). Anticipated adverse reactions with these lenses are the same as any other soft contact lens as listed in this study protocol Section 13.1. Due to the unique optical design of the RMY-100 lens, visual performance of these lenses may not be equivalent to that of lenses with a conventional spherical lens design. To manage the risk, special attention will be paid to visual acuity, visual complaints (eg, blurry vision or visual artifacts such as ghosting or haloes, etc.), and subjective visual acceptance while fitting the study lenses. In addition, the study lens power may be modified based on the refraction over the study lens and visual acuity. Finally, if lenses are to be dispensed for wear at home, specific criteria regarding visual acuity and subjective vision acceptance will be imposed so that no study lenses will be dispensed and the subject will be discontinued from the study unless these vision criteria are met. Because the current study is a non-dispensing study with the maximum lens exposure time for each subject being limited to less than 3 hours, risks associated with vision as a result of the unique optical design of the RMY-100 lens are minimal and potential long-term physiological/neurological impact are not applicable to this study.

Per the risk-to-benefit analysis, it is proposed that the benefits of slowing myopia progression outweigh the risks associated with daily disposable soft contact lens wear. Per the clinical study risk assessment, this study is considered a non-significant risk study based 1) the study is a non-dispensing study; and 2) although the investigational lens is optically designed for the intent of myopia control, the lens will be used in this study for myopia correction only with limited wear time (i.e., subjects will wear study lenses for less than 3 hours).

For the most comprehensive risk and benefit information regarding RMY-100 lenses refer to the latest version of the Investigator's Brochure for the RMY-100 lens.²⁶

1.5. Relevant Literature References and Prior Clinical Data Relevant to Proposed Clinical Study

The review of the scientific literature examined the current state of published information contact lens safety and myopia control with soft contact lenses. Potential applicable literature was identified through a literature search on PubMed.org dated back to 1980's, as well as through examination of review articles published on the subject. A list of relevant literature references is provided in latest version of the Investigator's Brochure for the RMY-100 lens.²⁶

To date, there have been a total of five clinical studies conducted during the development of the RMY-100 lenses.^{25,32-35} Among these studies, four were to evaluated the physiology responses and vision, comfort, handling and fit performances of the RMY-100 to ensure that the lens has satisfactory performances to be further evaluated in the long-term (up to 2 years), myopia control clinical trial in a pediatric population for the RMY-100. There were no serious, significant, or unanticipated ocular adverse events and no loss of best corrected visual acuity with wear of study test articles reported in these past clinical studies. For detailed information regarding prior clinical data refer to the latest version of the Investigator's Brochure for the RMY-100 lens.²⁶

2. STUDY OBJECTIVES, ENDPOINTS AND HYPOTHESES

2.1. Objectives

The objective of the study is to evaluate the on-eye optical performances of the RMY-100 lenses and comparing to the optical characteristics of eyes undergone orthokeratology treatment and with spectacle lens correction.

This is an exploratory study for providing information towards understanding the difference in optical impact between RMY-100 lens and orthokeratology and the mechanisms of orthokeratology for controlling myopia progression.

Primary Objective:

The primary objective of the study is to evaluate the on-eye optical performances of the RMY-100 lens, and compare with eyes treated with orthokeratology.

Secondary Objective:

The secondary objective of the study is to compare the on-eye optical performances of the RMY-100 lens with eyes wearing sphero-cylindrical correction in the spectacle trial frame.

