2.2. Endpoints

Primary Endpoint

The primary endpoint of this study is wavefront aberrations measured at 4-meter distance (0.25 D target vergence) and near (25 cm with 4 D target vergence).

Secondary Endpoint

The secondary endpoint of this study is Off-axis refraction at both temporal and nasal fields of retina at $\pm 10^{\circ}$, $\pm 20^{\circ}$, $\pm 30^{\circ}$ with targets at 4 meters and $\pm 30^{\circ}$ only with targets at 25 cm.

Other Exploratory Endpoints and observations include:

- Corneal and test article on-eye topography
- Accommodative response with target vergence of 0.25 D, 1 D, 2 D, 3 D and 4 D
- Slit lamp findings
- LogMAR visual acuity under HLHC, LLHC, and HLLC conditions
- Lens fit assessment
- Subjective vision assessment (CLUE Vision)

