2.3. Hypotheses

Primary Hypotheses:

- 1. After the 10-minute lens settling period, distance (4 meters) spherical aberration (Z_4^0) measured with RMY-100 on the eye will be similar or larger than that measured from the post-OK eyes.
- 2. After the 10-minute lens settling period, near (25 cm) spherical aberration (Z_4^0) measured with RMY-100 on the eye will be similar or larger than that measured from the post-OK eyes.

Secondary Hypotheses:

- 1. After the 10-minute lens settling period, distance (4 m) off-axis refraction at $\pm 30^{\circ}$ retinal eccentricity measured with RMY-100 on the eye will be similar or larger than that measured from the post-OK eyes.
- 2. After the 10-minute lens settling period, near (25 cm) off-axis refraction at $\pm 30^{\circ}$ retinal eccentricity measured with RMY-100 on the eye will be similar or larger than that measured from the post-OK eyes.

Other Hypotheses:

- 1. After the 10-minute lens settling period, the slope of accommodative response measured with RMY-100 on the eye will be similar as that measured from the post-OK eyes.
- 2. After the 10-minute lens settling period, distance (4 m) and near (25 cm) wavefront aberrations, off-axis refractions within $\pm 30^{\circ}$ retinal eccentricity, and the slope of accommodative response measured with RMY-100 on the eye will be different from that measured with spectacle trial lenses on eye.

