14. STATISTICAL METHODS

14.1. General Considerations

All data summaries and statistical analyses will be performed using the SAS software Version 9.4 (SAS Institute, Cary, NC). Throughout the analysis of data, the results for each subject/eye will be used when available for summarization and statistical analysis. Unscheduled visits will be summarized separately and will be excluded from the statistical analysis.

Summary tables (descriptive statistics and/or frequency tables) will be provided for all baseline variables, efficacy variables and safety variables as appropriate. Continuous variables will be summarized with descriptive statistics (n, mean, standard deviation [SD], median, minimum and maximum). Frequency count and percentage of subjects or eyes within each category will be provided for categorical data.

All statistical analysis will be conducted on the per-protocol population defined in Section 14.3.

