14.5. Primary Analysis

Primary efficacy analysis:

Distance and near wavefront aberration, specifically, spherical aberration (Z_4^0), will be analyzed using a linear mixed model. Each model will include the experimental design factors: treatment, distance and treatment by distance interaction and subject as random effect. Other baseline characteristics known of importance such as age and gender will be included as fixed covariates when appropriate. Kenward and Roger method will be used for the calculation of the denominator of degrees of freedom.³⁶

Comparisons between the treatment groups will be carried out using 95% confidence intervals constructed of least-square means (LSM) differences (RMY-100 minus OK) from the linear mixed models at each distance. Statistical difference will be concluded in the lower limit is greater than 0 or the upper limit is less than 0.

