14.6. Secondary Analysis

Secondary efficacy analysis:

Off-axis refraction at $\pm 30^{\circ}$ retinal eccentricities with targets at both distance (4 m) and near (25 cm) will be analyzed using a linear mixed model. Each model will include the experimental design factors: treatment, distance and treatment by distance interaction and subject as random effect. Other baseline characteristics known of importance such as age and gender will be included as fixed covariates when appropriate. Kenward and Roger method will be used for the calculation of the denominator of degrees of freedom.³⁶

Comparisons between the treatment groups will be carried out using 95% confidence intervals constructed of least-square means (LSM) differences (RMY-100 minus OK) from the linear

mixed models at each distance. Statistical difference will be concluded in the lower limit is greater than 0 or the upper limit is less than 0.

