14.10. Procedure for Reporting Deviations from Statistical Plan

The analysis will be conducted according to that specified in above sections. There are no known reasons for which it is planned to deviate from these analysis methods. If for any reason a change is made, the change will be documented in the study report along with a justification for the change.

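### The only secondary objective, RMY-100 versus spectacle correction, has no planned contrast in Section 14, although same-eye data for it are scheduled

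*Combined protocol and SAP*

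**What the plan says.** The Synopsis and Section 2.1 give a single secondary objective, to "compare the on-eye optical performances of the RMY-100 lens with eyes wearing sphero-cylindrical correction in the spectacle trial frame". Section 2.3 carries the matching prediction, but as the second of the Other Hypotheses: wavefront aberrations, off-axis refraction and the accommodative-response slope "measured with RMY-100 on the eye will be different from that measured with spectacle trial lenses on eye". The two hypotheses labelled secondary in 2.3 concern OK instead.

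Section 14 provides the following:

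- **14.5 (primary):** a mixed model for spherical aberration, with intervals for "least-square means (LSM) differences (RMY-100 minus OK" at each distance.
- **14.6 (secondary):** off-axis refraction at ±30° "retinal eccentricities with targets at both distance (4 m) and near (25 cm) will be analyzed using a linear mixed model", again with only the difference from OK defined.
- **14.1:** "Continuous variables will be summarized with descriptive statistics (n, mean, standard deviation [SD], median, minimum and maximum".
- **14.7:** summary statistics for the other observations, including accommodative response at five vergences. The slope is not mentioned.
- **14.10:** "The analysis will be conducted according to that specified in above sections". Any change is to be documented and justified in the study report.

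Section 14 does not mention spectacles.

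**The concern.** The analysis labelled secondary does not serve the objective labelled secondary. Section 14.6 answers the secondary hypotheses, which concern OK. The spectacle comparison has an objective and a hypothesis but no defined difference, interval or test.

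The descriptive tables do not fill the gap. With complete data, a mean difference could be found by subtracting one condition mean from the other. However, an SD for each condition does not determine the SD of the within-eye differences, so the planned tables alone cannot give a valid paired interval. The study report could therefore follow the plan exactly and still say nothing inferential about a named objective. A contrast added later would have to be reported as a change from plan.

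**Working it through.** The plan states no SD, correlation, effect size or power for this comparison (14.2 says the sample size rests on no power analysis), so there is no figure to reproduce. The check has three parts.

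**1. Are the paired data scheduled?** Yes, for all three measures named in the hypothesis. All are in Test subjects, OD only, with three repeats per condition (Section 7.2):

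| Measure | Visit 1, trial frame | Visit 2, RMY-100 |
|---|---|---|
| Wavefront, 4 m and 25 cm | step 1.12 | step 2.16 |
| Accommodative response, 0.25, 1, 2, 3 and 4 D | step 1.13 | step 2.17 |
| Off-axis ±10°, ±20°, ±30° at 4 m; ±30° at 25 cm | step 1.14 | step 2.18 |

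The per-protocol population in 14.3 requires completion of all visits, so a Test subject in that population should supply both halves of each pair.

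**2. What precision would the contrast have?** Section 4.3 targets at least 20 Test completers from about 25 enrolled. The paired 95% half-width is t(0.975, n−1) / √n × SDd, where SDd is the SD of the within-eye difference.

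- n = 20: 2.093 / √20 = 0.468 SDd
- n = 25: 2.064 / √25 = 0.413 SDd

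Restating this in single-condition SD units needs assumptions that the documents do not supply. With equal SDs in the two conditions and an assumed within-eye correlation ρ, SDd = SD × √(2(1−ρ)). At n = 20 the half-width is then:

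| Assumed ρ | 0 | 0.3 | 0.5 | 0.7 | 0.9 |
|---|---|---|---|---|---|
| Half-width (SD) | 0.66 | 0.55 | 0.47 | 0.36 | 0.21 |

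This range is illustrative. The figures in SDd units need no assumed correlation.

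**3. How many intervals would the contrast add?** Spherical aberration gives 2 (4 m and 25 cm). Off-axis refraction gives 6 at 4 m and 2 at 25 cm. The slope gives 1. The total is 2 + 6 + 2 + 1 = 11. If they were independent and all true differences were zero, the chance that at least one interval excludes zero is 1 − 0.95^11 = 0.43.

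**The case against.** The strongest reply is that nothing is lost. Section 14.2 says that the data collected, not the summary tables, will inform later trials. The same-eye values exist, and the instrument exports go to the sponsor (15.1). Section 14.9 also mentions listings, although it does not say whether they hold subject-level values. A reader might infer that the paired SD would be unavailable for future design. The documents do not support that, because it can be computed from the data at any time.

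A reader might also infer that the plan would yield intervals several times too wide. That would require someone to treat the two conditions as independent groups. No such interval is planned, and its excess width would depend on an assumed correlation.

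Three further points have some weight:

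- **The model could carry the comparison.** The treatment factor in 14.5 and 14.6 has no stated levels, and subject is a random effect, so a spectacle level could be added. Neither that level nor the contrast is stated, so the gap remains, but the remedy may be brief.
- **Descriptive treatment can be defended.** The study is exploratory, and the spectacle hypothesis sits in the lowest tier, which receives summary statistics. The objective, however, is labelled secondary, and the same exploratory plan gives intervals for the OK contrast.
- **Section 14.10 permits documented changes.** This makes a later analysis allowable, but it does not make it planned.

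Section 14.6 also leaves out ±10° and ±20°. For the OK comparison that is a separate matter and does not bear on this point.

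**Conclusion.** The point stands in a limited form. The only secondary objective has no planned contrast, paired SD or interval, and the secondary analysis addresses a different comparison. This rests on the text of Sections 2.1, 2.3 and 14 and needs no numerical assumption.

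The consequence is an objective left unanswered in the planned analysis. It is not lost data and not a wrong conclusion: no decision rule or power claim depends on the comparison, and the primary analysis is unaffected. The scheduled pairs would support a 95% half-width of 0.47 SDd at n = 20 or 0.41 SDd at n = 25. It is worth correcting before analysis, because the plan cannot otherwise answer a question that it sets itself.

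**What to change.** Add to Section 14 an exploratory within-subject contrast, RMY-100 minus spectacle, in Test subjects (OD), on the per-subject mean of the three repeats. Report the mean difference, paired SD and 95% interval for:

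- spherical aberration Z(4,0) at 4 m and at 25 cm;
- off-axis refraction at the angles collected under both conditions (±10°, ±20° and ±30° at 4 m; ±30° at 25 cm), on the same measure as in 14.6;
- the accommodative-response slope, computed per subject and condition over the five vergences.

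Equivalently, add spectacle as a treatment level in a mixed model and name the contrast. The model must respect the within-subject pairing. A random subject intercept alone forces one common correlation across a subject's conditions and distances, so use a richer covariance or a separate paired analysis at each distance.

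Align the tiers, so that the spectacle objective and its hypothesis are both secondary or both other.

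State these limits with the result:

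- The roughly 11 intervals are unadjusted and exploratory, as 14.4 allows, with about a 43% chance of at least one false exclusion of zero if independent.
- Condition is confounded with visit, in a fixed and unmasked order. Bare-eye wavefront at 4 m is taken at both visits (steps 1.12 and 2.7), which allows a partial check of visit drift for that measure.
- The conditions differ in cylinder correction (the trial frame is sphero-cylindrical, RMY-100 is spherical, and eligibility allows up to 1.00 D) and in residual over-refraction (step 2.14 allows some subjects to continue at −0.25 D).

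The cost is a paragraph in Section 14, the extra analyses and the added unadjusted intervals. Visits, procedures and sample size do not change.
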